### **6.3.2 Lenalidomide Administration (Rd Concomitant Cohort Only)**

Lenalidomide will be administered as a single, daily oral dose of 25 mg/day on Days 1 to 21 for 21 consecutive days followed by one week rest period in a 28-day cycle. This cycle will be repeated.

Lenalidomide should be taken at approximately the same time each day. Patients should be instructed to swallow lenalidomide capsules whole with water and not to break, chew, or open the capsules.

Lenalidomide and MLN9708 should be taken simultaneously. Lenalidomide should be used according to the package insert of CCI 5 mg.

A missed dose of lenalidomide can be taken as soon as the patient remembers provided that it is within 12 hours from the regular dosing schedule. A double dose should not be taken to make up for a missed dose. If enough time has elapsed that the missed dose is not taken within the same day, the missed dose should be skipped. If the patient vomits after taking a dose, the patient should not repeat the dose but should resume dosing at the time of the next schedule.

### **6.3.3 Dexamethasone Administration (Rd Concomitant Cohort Only)**

Dexamethasone will be administered as a single, oral dose of 40 mg/day weekly on Days 1, 8, 15, and 22 of a 28-day cycle.

Dexamethasone will be taken at approximately the same time each day, approximately 1 hour after MLN9708 and lenalidomide. Each dose of dexamethasone should be taken with food or milk. Dexamethasone should be used according to the package insert of CCI 4 mg.

Missed doses of dexamethasone can be taken as soon as the patient remembers provided that at least 3 days elapses between doses (until Day 4). If the patient vomits after taking a dose, the patient should not repeat the dose but resume dosing at the time of the next schedule.

## **6.4 Criteria for Beginning the Next Cycle of Treatment**

### **6.4.1 MLN9708 Monotherapy**

Treatment with MLN9708 will be repeated every 28 days as 1 cycle. For a new treatment cycle to begin, the patient must satisfy the following criteria:

- ANC must be  $\geq 1,000 \text{ mm}^3$
- Platelet count must be  $\geq 50,000 \text{ mm}^3$
- All other toxicity (except for alopecia) considered related to MLN9708 must be resolved to  $\leq$  Grade 1 or to the patient's baseline values

#### **6.4.2 MLN9708 in Combination With Rd**

Treatment of MLN9708 with Rd will be repeated every 28 days as 1 cycle. For a new treatment cycle to begin, the patient must satisfy the following criteria:

- ANC must be  $\geq 1,000 \text{ mm}^3$
- Platelet count must be  $\geq 75,000 \text{ mm}^3$
- All other nonhematological toxicities (except for alopecia) considered related to MLN9708 or Rd must be resolved to  $\leq$  Grade 1 or to the patient's baseline values

#### **6.4.3 Criteria for Dose Delays**

If a subject fails to meet the criteria for beginning the next cycle of treatment, initiation of the next cycle should be delayed for one week for re-evaluation. If the subject still fails to meet the criteria, the subject should be re-evaluated weekly. The next cycle treatment can be initiated if the subject meets the criteria for initiating the next cycle within 3 weeks of the scheduled initiation of the next cycle. The MLN9708 and lenalidomide starting doses for the next cycle are presented below.

- Reinitiate with one dose level reduction
  - If MLN9708 or lenalidomide treatment was interrupted during the preceding cycle in accordance with “[6.5 Dose Modification](#)” and treatment could not be resumed within the same cycle
- Reinitiate with the same dose level as the preceding cycle
  - If there was no need for dose adjustment in the preceding cycle
  - If MLN9708 or lenalidomide treatment was interrupted during the preceding cycle in accordance with “[6.5 Dose Modification](#)” and treatment could be resumed during the cycle

Should the start of the next cycle need to be delayed for more than 3 weeks because of incomplete recovery from treatment-related toxicity, the patient undergoes the EOS exams, and treatment should be discontinued.

## 6.5 Dose Modification

### 6.5.1 MLN9708 Monotherapy

#### 6.5.1.1 Criteria for Dose Modification

Dose modifications of MLN9708 are not permitted in Cycle 1.

If dose modification is required in Cycle 2 or subsequent cycles, MLN9708 dose will be reduced by one level according to [Table 6-2](#). If multiple toxicities are noted, the dose should be interrupted or reduced according to the most severe toxicity guidelines ([Table 6-3](#) and [Table 6-4](#)). Toxicity will be assessed according to the Common Terminology Criteria for Adverse Events (CTCAE) version 4.03.

**Table 6-2. Dose Reduction Levels of MLN9708**

Initial dose	Level 1	Level 2	Level 3	Level 4
4.0 mg	3.0 mg	2.3 mg	Discontinue	-
5.5 mg	4.0 mg	3.0 mg	2.3 mg	Discontinue

#### 6.5.1.1.1 Dose Modification for Hematological Toxicity

If platelet count is less than 30,000/mm^3 or ANC is less than 750/mm^3 in Cycle 2 or subsequent cycles, MLN9708 dose should be interrupted. If the platelet count is recovered to at least 30,000/mm^3 and ANC is recovered to at least 750/mm^3 within the same cycle, MLN9708 may be reinitiated with one dose level reduction. If the subject meets the criteria for retreatment by delaying the initiation of the subsequent cycle, the subjects may be retreated with MLN9708 with one dose level reduction (See “[6.4 Criteria for Beginning the Next Cycle of Treatment](#)”).

**Table 6-3. Dose Modification of MLN9708 for Hematological Toxicities**

Criteria	Action
Within-cycle Dose Modifications (Days 8 and 15)	
If platelet count < 30,000/mm  or ANC < 750/mm 	Interrupt MLN9708, follow CBC weekly. Upon recovery, MLN9708 may be reinitiated with one dose level reduction.

ANC = absolute neutrophil count, CBC = complete blood count

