## **6.3 Dosage, administration method, dosing schedule**

### **6.3.1 MLN9708 administration**

In this study, MLN9708 will be administered orally once weekly for 3 weeks (on Days 1, 8, and 15 and skip Day 22) in a 28-day cycle for up to 12 cycles.

MLN9708 will be taken on an empty stomach at least 1 hour before or no sooner than 2 hours after a meal.

In Cycle 1, MLN9708 will be given according to the dosage and administration specified in this study protocol; no interruption, delays, or reduction will be permitted.

Missed doses of MLN9708 in Cycle 2 and subsequent cycles can be taken as soon as the patient remembers provided that at least 3 days elapses between doses (until Day 4). If a patient vomits after taking MLN9708, the patient should not repeat the dose, but resume dosing at the time of the next schedule.

Once a dose is reduced, no re-escalation will be permitted.

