**Table 6-6. MLN9708 and Lenalidomide Dose Modification for Thrombocytopenia**

Platelets	Action
First fall to $< 30,000/\text{mm}^3$	Interrupt lenalidomide treatment, follow CBC weekly
Return to $\geq 30,000/\text{mm}^3$ within the same cycle	Resume lenalidomide at 15 mg
Second fall: Subsequent drop below $30,000/\text{mm}^3$	Interrupt MLN9708, follow CBC weekly
Return to $\geq 30,000/\text{mm}^3$ within the same cycle	Resume MLN9708 at reduced dose by 1 level (Level 1)
Third fall: Subsequent drop below $30,000/\text{mm}^3$	Interrupt lenalidomide treatment, follow CBC weekly
Return to $\geq 30,000/\text{mm}^3$ within the same cycle	Resume lenalidomide at 10 mg
Fourth fall: Subsequent drop below $30,000/\text{mm}^3$	Interrupt MLN9708, follow CBC weekly
Return to $\geq 30,000/\text{mm}^3$ within the same cycle	Resume MLN9708 at reduced dose by 1 level (Level 2)
	Do not dose MLN9708 below 2.3 mg
Fifth fall: Subsequent drop below $30,000/\text{mm}^3$	Interrupt lenalidomide, follow CBC weekly
Return to $\geq 30,000/\text{mm}^3$ within the same cycle	Resume lenalidomide at 5 mg
	Do not dose lenalidomide below 5 mg

CBC = complete blood count

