### **7.2.2 Treatment period**

Study treatment must be initiated within 7 days after enrollment. If study treatment cannot be initiated within 7 days, the patient may be rescreened after obtaining additional informed consent. For details, see “[5 SUBJECT ENROLLMENT](#).” Hospitalization is generally required from the first dose of MLN9708 through the start of Cycle 2. However, if a subject wishes to return home temporarily and the investigator confirms that the subject’s symptoms are stable based on the available data collected in the study to that point, then the subject may return home temporarily, provided this does not interfere with the study observations/tests.

See “[6.3 Dosage, administration method, dosing schedule](#)” for more details on the administration of MLN9708 and Rd. Unless otherwise specified, the following procedures must be followed before administering MLN9708 in each cycle. See [Appendix A](#) for the acceptable test, observation, and examination time windows.

- Obtaining informed consent to extended treatment
  - Written consent to the extended administration of MLN9708 will be obtained prior to Cycle 2 treatment from subjects who meet the criteria specified in “[6.4 Criteria for Beginning the Next Cycle of Treatment](#)” and who have experienced no safety concerns.

- Medical interview (including confirmation of treatment compliance): Day 1 of each Cycle
- ECOG performance status: See [Appendix B](#)
  - Cycle 1: Days 1, 8, and 15
  - Cycles 2 and subsequent cycles: Day 1
- Vital signs (sitting blood pressure, pulse rate and axillary temperature, SpO2)
  - Cycle 1: Days 1, 8 and 15
  - Cycles 2 to 12: Days 1 and 15
  - Cycle 13 and subsequent cycles: Day 1
- Body weight
  - Cycle 1: Before MLN9708 dosing on Day 1. If a patient's body weight at screening is measured within 3 days before the first dose, then this measurement may be used for the Cycle 1 Day 1 data.
  - Cycle 2 and subsequent cycles: Day 1 of each cycle. Measurements taken within 3 days before dosing will be accepted.
- 12-lead ECG (QRS, QT, QTc, PR and heart rate)
  - Day 1 of Cycle 1: Before dosing
  - Day 15 of Cycle 1: Before dosing, 30 minutes ( $\pm$  10 min) after dosing, 1 hour ( $\pm$  15 min) after dosing, and 4 hours ( $\pm$  45 min) after dosing
  - Day 16 of Cycle 1: 24 hours ( $\pm$  1 hr) after dosing on Day 15
- Laboratory tests: See [Table 7-1](#) for the test parameters.
  - Hematology tests
    - Cycle 1: Days 1, 8, 15 and 22

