    - Cycles 2 and 3: Days 1, 8 and 15
    - Cycles 4 to 12: Days 1 and 15
    - Cycle 13 and subsequent cycles: Day 1

If a screening test is performed within 3 days before the first dose, the results may be used as the Cycle 1 Day 1 data.
  - Chemistry tests
    - Cycle 1: Days 1, 8, 15 and 22
    - Cycles 2 and 3: Days 1, 8 and 15
    - Cycles 4 to 12: Days 1 and 15
    - Cycle 13 and subsequent cycles: Day 1

If a screening test is performed within 3 days before the first dose, the result may be used as the data as Cycle 1 Day 1 data. Hemoglobin A1c (HbA1c) will be measured only on Day 1 of each cycle.

- Urinalysis: Day 1 of each cycle
- Immunoglobulin quantitation (IgG, IgM, IgA, IgD): Day 1 of each cycle
- FLC: FLC will be measured as appropriate if a response assessment requires confirmation or disease progression is suspected (see [Appendix G](#)).
- Serum M-protein (electrophoresis protein fraction test): Performed on Day 1 of each cycle. If a screening test is performed within 7 days before the first dose, the results may be used as the Cycle 1 Day 1 data.
- Urine M-protein (electrophoresis protein fraction test):

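### The monotherapy rule that interrupts MLN9708 for low counts on Days 8 and 15 has no scheduled Day 8 count from Cycle 4, and no scheduled Day 8 or Day 15 count from Cycle 13

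*Protocol*

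**What the plan says.** **Dosing.** Protocol 6.3.1: "MLN9708 will be administered orally once weekly for 3 weeks (on Days 1, 8, and 15 and skip Day 22) in a 28-day cycle". That section plans up to 12 cycles, but 3.1 and 3.4.1 let subjects continue beyond Cycle 12.

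**Rule, monotherapy.** Under 6.5.1.1.1, if platelets are below 30,000/mm³ or ANC is below 750/mm³ "in Cycle 2 or subsequent cycles, MLN9708 dose should be interrupted". Table 6-3 gives the same thresholds under "Within-cycle Dose Modifications (Days 8 and 15". Neither place sets an upper cycle limit. The weekly counts that Table 6-3 adds follow an interruption.

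**Rule, Rd cohorts.** Tables 6-6 and 6-7 act on successive falls (platelets below 30,000/mm³, ANC below 1,000/mm³) and on recovery within the same cycle. They name no dosing days. A first fall interrupts lenalidomide, and MLN9708 may stay unchanged.

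**Scheduled hematology (7.2.2).** The first cycle has a count every week through Day 22, and the second and third cycles have one on each of the three dosing days. Day 8 then drops out: "Cycles 4 to 12: Days 1 and 15". Later the Day 15 count goes as well, and the schedule that remains reads "Cycle 13 and subsequent cycles: Day 1".

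**Start of a cycle.** Section 6.4 has its own Day 1 criteria: ANC of at least 1,000/mm³, with platelets of at least 50,000/mm³ (monotherapy) or 75,000/mm³ (Rd).

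**The concern.** A rule that depends on a blood count needs a count to act on. Table 6-3 is written for two dosing days in every cycle from Cycle 2, whereas the schedule that should supply the counts thins out twice. Nothing found in the protocol says what the rule rests on once the count for that day is no longer planned.

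Thrombocytopenia and neutropenia are named risks in 1.5.1. A subject treated exactly as scheduled could take a Day 8 dose (from Cycle 4) or a Day 15 dose (from Cycle 13) at a count for which the protocol calls for interruption, and nobody would know. The effect can carry forward: 6.4.3 sets the next cycle's starting dose partly by whether treatment was interrupted in the preceding cycle, and a fall that was never measured leaves no interruption on record.

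**Working it through.** The plan states no figure to reproduce. The check sets the doses covered by the within-cycle rule against the scheduled counts.

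**Inputs**
- Doses under the rule: Days 8 and 15 of each cycle from Cycle 2 (6.3.1, 6.5.1.1.1, Table 6-3). Day 1 doses are left out because 6.4 governs them.
- Scheduled counts: the hematology days in 7.2.2.

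**Formula**
- Doses under the rule = cycles × 2.
- Doses without a count = those whose day is not a scheduled hematology day in that cycle.

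| Cycles | Scheduled count days | Doses under the rule | With a scheduled count | Without |
|---|---|---|---|---|
| 2–3 | 1, 8, 15 | 2 × 2 = 4 | 4 | 0 |
| 4–12 | 1, 15 | 9 × 2 = 18 | 9 (all Day 15) | 9 (all Day 8) |
| 2–12 together | – | 4 + 18 = 22 | 4 + 9 = 13 | 9 (9/22 = 41%) |
| 13 onward, per cycle | 1 | 2 | 0 | 2 |

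**Time from the last scheduled count to an uncovered dose**
- Day 8 dose: 8 − 1 = 7 days.
- Day 15 dose from Cycle 13: 15 − 1 = 14 days.

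**Longest gap between scheduled counts**
- Cycles 2–3: Day 15 to the next Day 1, 29 − 15 = 14 days.
- Cycles 4–12: 15 − 1 = 14 and 29 − 15 = 14, so 14 days.
- Cycle 13 onward: 29 − 1 = 28 days.

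Losing Day 8 in Cycle 4 therefore does not lengthen the longest gap. It removes the count on a day for which the rule is written. Losing Day 15 in Cycle 13 does both.

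**Does anything else supply the count?** The weekly counts in Tables 6-3, 6-6 and 6-7 start once a fall has been found. The Day 1 count serves 6.4, which has different thresholds in monotherapy. No section found requires a count before the Day 8 dose from Cycle 4 or the Day 15 dose from Cycle 13. The Appendix A table is not in the public text. Its footnote q, as given in the version 2.1 change memo, limits Day 15 hematology to the first 12 cycles, which agrees with 7.2.2.

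**The case against.** The rule is conditional: it acts on any low count, scheduled or not. Section 6.8 lets investigators perform procedures needed for supportive care, and 1.5.1 asks that recovery of blood counts be monitored. The thinner schedule looks deliberate, because 7.2.2 and the version 2.1 change memo agree on it. In monotherapy, every cycle starts only with counts above both interruption thresholds (platelets 50,000 against 30,000/mm³, ANC 1,000 against 750/mm³). The documents give no rate of within-cycle falls after Cycle 3, so the actual risk is not shown.

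All of this stands, and it limits the point. A reader might infer that the rule cannot be followed at all. The documents do not support that, since an unscheduled count would trigger it. But none of it gives the rule a planned value, and nothing found says that an uncovered dose is meant to go ahead without one.

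Other stronger readings also fail:
- **Both days uncovered from Cycle 4.** Day 15 has a scheduled count through Cycle 12.
- **9 of 27 doses, or 2 of 3 per cycle.** These denominators include Day 1 doses, which the within-cycle rule does not cover.
- **The same defect, day for day, in the Rd cohorts.** Tables 6-6 and 6-7 name no days, and a first fall need not change MLN9708. They share the hematology schedule, and the point goes no further than that.
- **A matching gap in vital signs.** Those omit Day 8 from Cycle 2 already, and no hematological rule depends on them.
- **A biased SAP comparison.** SAP 9.4.3.2 tabulates worst post-baseline grade and maximum shift over the whole treatment period. It plans no comparison of early with late cycles, and line plots by subject and a listing of Grade 3 or higher abnormalities are already planned.

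DLT assessment is not affected: it rests on Cycle 1, which has weekly counts.

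**Conclusion.** The mismatch is real and limited. For a monotherapy subject treated through Cycle 12 without missed doses, half of the doses under the within-cycle rule in Cycles 4 to 12 (9 of 18, all on Day 8) have no scheduled count. From Cycle 13 none of them has one (0 of 2 per cycle). The Rd cohorts are affected only in that their within-cycle falls are looked for on the same schedule.

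This assumes that Table 6-3 means a count for the dosing day in question, and that Appendix A adds no hematology days beyond 7.2.2. It makes no claim about how often a low count would be missed, because the documents do not allow that estimate. It is a safety inconsistency between sections of the protocol, and no planned analysis has to change because of it.

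**What to change.** Reconcile 6.5.1.1.1 and Table 6-3, and with them Tables 6-6 and 6-7, with the hematology schedule in 7.2.2 and Appendix A, so that each within-cycle rule and the scheduled counts agree in every cycle in which treatment is allowed. The sponsor decides which passage governs, and the amended text should say so. This review does not recommend either direction.

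The cost is a protocol amendment to a few lines. If the sponsor keeps the schedule, only wording changes. If it changes the schedule, the uncovered doses number one per cycle in Cycles 4 to 12 and two per cycle from Cycle 13. No SAP change is needed.

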### 6.5.1.1.2 Dose Modification for Non-hematological Toxicity

If non-hematological toxicities shown in [Table 6-4](#) occur in Cycle 2 and subsequent cycles, MLN9708 should be interrupted. Upon recovery, MLN9708 may be reinitiated with one dose level reduction. For Grade 4 non-hematological toxicities, MLN9708 should be discontinued permanently.

**Table 6-4. Dose Modification of MLN9708 for Non-hematological Toxicities**

Criteria	Action
Peripheral Neuropathy: Grade 2 peripheral neuropathy with pain	MLN9708 therapy should be interrupted until toxicities have resolved to $\leq$ Grade 1 or baseline. Upon recovery, MLN9708 may be reinitiated with one dose level reduction.
Grade 3 non-hematological toxicities	MLN9708 therapy should be interrupted until toxicities have resolved to $\leq$ Grade 1 or baseline. Upon recovery, MLN9708 may be reinitiated with one dose level reduction.
Grade 4 non-hematological toxicities	Discontinue MLN9708.  With agreement by the sponsor, investigators may consider restarting the therapy for patients continue to clinically benefit from the therapy.

## 6.5.2 MLN9708 in combination with Rd

### 6.5.2.1 Criteria for Dose Modification

Dose modifications of MLN9708 are not permitted in Cycle 1. Dose modifications of Rd should be avoided as much as possible. If a subject experiences an adverse event(s) considered strongly related to lenalidomide or dexamethasone and the investigator considers it difficult to continue the treatment with Rd, the investigator and the sponsor will discuss the alternative dose modification.

If dose modification is required in Cycle 2 or subsequent cycles, MLN9708, lenalidomide, or dexamethasone dose will be modified levels according to [Table 6-5](#). If multiple toxicities are noted, the dose should be modified or delayed according to the most severe toxicity guidelines ([Table 6-6](#) through [Table 6-11](#)). Once a dose is reduced, no re-escalation will be permitted.

Each adverse event should be attributed to a specific drug, if possible, so that the dose can be modified accordingly. Reduction of one agent and not the other is appropriate if toxicity is related primarily to one of the agents. Toxicity will be assessed according to the CTCAE version 4.03.

**Table 6-5. Dose Reduction Levels for MLN9708, lenalidomide and dexamethasone**

Drug	Initial dose	Level 1	Level 2	Level 3	Level 4
MLN9708	4.0 mg	3.0 mg	2.3 mg	Discontinue	-
	5.5 mg	4.0 mg	3.0 mg	2.3 mg	Discontinue
lenalidomide	25 mg	15 mg	10 mg	5 mg	Discontinue
dexamethasone	40 mg	20 mg	8 mg	Discontinue	-

## **6.5.2.2 Dose Modification for Hematological Toxicity**

### **6.5.2.2.1 Dose Modification for Thrombocytopenia**

If platelet count is less than 30,000/mm^3 in Cycle 2 or subsequent cycles, lenalidomide dose should be interrupted. If the platelet count is recovered to at least 30,000/mm^3 within the same cycle, lenalidomide may be reinitiated with one dose level reduction. MLN9708 dose can be kept as is. If the subject meets the criteria for retreatment with delaying the initiation of the subsequent cycle, the subjects may be retreated with lenalidomide with one dose level reduction (See [“6.4 Criteria for Beginning the Next Cycle of Treatment”](#)).

If thrombocytopenia occurs more than once, MLN9708 or lenalidomide dose will be modified at each occurrence according to [Table 6-6](#) to continue the treatment. In some severe situations, both MLN9708 and lenalidomide may be interrupted or reduced if needed based on discussion between the investigator and the sponsor.

**Table 6-6. MLN9708 and Lenalidomide Dose Modification for Thrombocytopenia**

Platelets	Action
First fall to $< 30,000/\text{mm}^3$	Interrupt lenalidomide treatment, follow CBC weekly
Return to $\geq 30,000/\text{mm}^3$ within the same cycle	Resume lenalidomide at 15 mg
Second fall: Subsequent drop below $30,000/\text{mm}^3$	Interrupt MLN9708, follow CBC weekly
Return to $\geq 30,000/\text{mm}^3$ within the same cycle	Resume MLN9708 at reduced dose by 1 level (Level 1)
Third fall: Subsequent drop below $30,000/\text{mm}^3$	Interrupt lenalidomide treatment, follow CBC weekly
Return to $\geq 30,000/\text{mm}^3$ within the same cycle	Resume lenalidomide at 10 mg
Fourth fall: Subsequent drop below $30,000/\text{mm}^3$	Interrupt MLN9708, follow CBC weekly
Return to $\geq 30,000/\text{mm}^3$ within the same cycle	Resume MLN9708 at reduced dose by 1 level (Level 2)
	Do not dose MLN9708 below 2.3 mg
Fifth fall: Subsequent drop below $30,000/\text{mm}^3$	Interrupt lenalidomide, follow CBC weekly
Return to $\geq 30,000/\text{mm}^3$ within the same cycle	Resume lenalidomide at 5 mg
	Do not dose lenalidomide below 5 mg

CBC = complete blood count

#### **6.5.2.2.2 Dose Modification for Neutropenia**

If ANC count is less than  $1,000/\text{mm}^3$  in Cycle 2 or subsequent cycles, lenalidomide dose should be interrupted. If the ANC is recovered to at least  $1,000/\text{mm}^3$  within the same cycle, lenalidomide may be reinitiated with one dose level reduction. MLN9708 dose can be kept as is. If the subject meets the criteria for retreatment by delaying the initiation of the subsequent cycle, the subjects may be retreated with lenalidomide with one dose level reduction (See section “[6.4 Criteria for Beginning the Next Cycle of Treatment](#)”).

If neutropenia occurs more than once, MLN9708 or lenalidomide dose will be modified according to [Table 6-7](#) to continue the treatment. G-CSF is not permitted in Cycle 1 unless Grade 4 neutropenia occurs (See section [6.9 Excluded Concomitant Medications and Procedures](#)). In some severe situations, both lenalidomide and MLN9708 may be interrupted or reduced if needed based on discussion between the investigator and the sponsor.

